### 13.2.4. Data quality assurance

The sponsor will permit audits and regulatory agency inspections.

### 13.2.5. Publication policy

GSK aims to submit the results of the study for publication in searchable, peer reviewed scientific literature and follow the guidance from the International Committee of Medical Journal Editors (ICMJE).

219111 (EPI-ZOSTER-097 VE US DB) Protocol Final

## 13.3. Appendix 3 Appendix Data types

Specific information in the OptumTM database includes, but is not limited to, the following types of data:

- Enrollment data.
  - A unique identifier received from the insurer, which is linkable to all other data.
  - Possible multiple enrolments with the same insurer; the length of each given enrollment "span" may vary substantially.
- Demographic data.
  - Birth date, sex, race/ethnicity, and ZIP code of their most recently recorded primary residence.
- Medical encounter data.
  - The healthcare provider, facility of the encounter, admission and discharge dates, encounter type (ambulatory visit, emergency visit, inpatient hospital stay).
- Pharmacy dispensing data.
  - Date of each dispensed prescription, the NDC identifier associated with the dispensed product, the nominal days' supply, and the number of dispensed individual units (pills, tables, vials, etc.). (Over the counter medications are not captured in the databases.)
- Diagnosis data.
  - Date of diagnosis with associated encounter identifier, admission date, provider identifier.
  - Encounter type, diagnoses with ICD-9-CM, and ICD-10-CM codes.
- Procedure data.
  - Date of procedure, associated encounter identifier, admission date, provider identifier, and encounter type.
  - Codes: ICD-9-CM and ICD-10-CM, CPT categories (II, III, or IV), revenue.

## 13.4. Appendix 4: ICD-10 codes

## 13.4.1. Codes to identify auto-immune diagnoses

The following ICD-10 codes will be used to define the auto-immune population:

ICD-10	AID	Description
M32.X	SLE	Systemic lupus erythematosus
G35.X	MS	Multiple sclerosis
M05.X	RA	Rheumatoid arthritis with rheumatoid factor
M06.X		Other rheumatoid arthritis
K50.X	IBD	Crohn's disease
K51.X		Ulcerative colitis
L40.X	PsO	Psoriasis
L40.5	PsA	Psoriatic arthritis

Codes will be updated as needed if additional codes are identified.

### 13.4.2. Codes and medications for the diagnosis of herpes zoster

	Diagnosis code or medication generic names	
Codes/medications for herpes zoster diagnosis		
Herpes Zoster	B02.xx	
Medications to treat herpes zoster	Acyclovir, valacyclovir, or famciclovir	

Codes will be updated as needed if additional codes are identified.

## 13.4.3. Codes to identify the use of zoster vaccine

The following Current Procedural Terminology (CPT) code will be used to retrieve Shingrix vaccinations:

Code	Description	Vaccine type
90750	Zoster (shingles) vaccine (HZV), recombinant, subunit,	Shingrix
	adjuvanted, for intramuscular use	

Codes will be updated as needed if additional codes are identified.

219111 (EPI-ZOSTER-097 VE US DB) Protocol Final

The following National Drug Codes (NDCs) codes will be used to retrieve Shingrix vaccinations:

Code	description	vaccine type
58160-082-311	Zoster vaccine recombinant, adjuvanted	Shingrix
58160-081-912	Zoster vaccine recombinant, adjuvanted	Shingrix
50090-514-700	Zoster vaccine recombinant, adjuvanted	Shingrix
58160-082-801	Varicella-zoster ge vac,2 of 2	Shingrix
50090-337-200	Zoster vaccine recombinant, adjuvanted	Shingrix
58160-082-803	Varicella-zoster ge vac,2 of 2	Shingrix

Codes will be updated as needed if additional codes are identified.

# 13.4.4. CPT/HCPCS codes used to identify influenza vaccinations

CPT/H CPCS Code	Description
90630	Vaccine for influenza for injection into skin, quadrivalent, preservative free
90653	Vaccine for influenza for injection into muscle, inactivated, subunit, adjuvanted
90654	Vaccine for influenza injection into skin, trivalent, preservative free
90656	Vaccine for influenza for administration into muscle, 0.5 ml dosage, trivalent, preservative free
90658	Vaccine for influenza for administration into muscle, 0.5 ml dosage, trivalent
90661	Vaccine for influenza for administration into muscle, 0.5 ml dosage, trivalent, cell culture-based
90662	Vaccine for influenza for injection into muscle, split virus, enhanced immunogenicity via increased antigen content
90673	Vaccine for influenza administered into muscle, preservative and antibiotic free, trivalent, recombinant DNA-derived
90674	Vaccine for influenza for administration into muscle, 0.5 ml dosage, tetravalent, cell-culture based
90682	Influenza virus vaccine, quadrivalent (RIV4), derived from recombinant DNA, hemagglutinin (HA) protein only, preservative and antibiotic free, for intramuscular use)
90686	Vaccine for influenza for administration into muscle, 0.5 ml dosage, quadrivalent, preservative free
90688	Vaccine for influenza for administration into muscle, 0.5 ml dosage, quadrivalent
90756	Influenza virus vaccine, quadrivalent (ccIIV4), derived from cell cultures, subunit, antibiotic free, 0.5mL dosage, for intramuscular use)
G0008	Administration of influenza virus vaccine
Q2034	Influenza virus vaccine, split virus, for intramuscular use (agriflu)
Q2035	Influenza virus vaccine, split virus, when administered to individuals 3 years of age and older, for intramuscular use (afluria)
Q2036	Influenza virus vaccine, split virus, when administered to individuals 3 years of age and older, for intramuscular use (flulaval)
Q2037	Influenza virus vaccine, split virus, when administered to individuals 3 years of age and older, for intramuscular use (fluvirin)
Q2038	Influenza virus vaccine, split virus, when administered to individuals 3 years of age and older, for intramuscular use (fluzone)
Q2039	Influenza virus vaccine, not otherwise specified

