- 7. Healthy-user bias: Participants receiving RZV, or other vaccines may be healthier or have other behaviors leading to improved health compared to their unvaccinated matches. This bias may lead vaccinated participants to have lower rates of HZ in the study. The study will capture and adjust for variables related to healthy users, such as use of other vaccinations, to minimize this bias.
- 8. Duplicate health care claims: A beneficiary of OptumTM may be a beneficiary of more than one insurance product at a time or switch to a new insurance product before departing from another, resulting in duplicate health care claims and multiple lines per participant. Also, when time periods overlap, a clean link between claims and the eligibility table may be absent because multiple rows may be returned in a match. While there is a risk of this happening, the number of multiple health care claims and their impact is expected to be negligible.
- 9. Limited follow-up period: While the ability to assess durability of VE at extended time points is limited, this is an open cohort study that will allow vaccinated and unvaccinated participants to come in late or die during the follow-up period; this is not expected to impact the overall incidence rate of HZ. In addition, participants entering the cohort in early 2018 could have 4 years of follow-up.
- 10. Generalizability: The population in OptumTM have racial/ethnic diversity, and the age distribution of participants with selected AIDs in this claims database are expected to reflect the distribution nationally. The practices of care for participants with selected AIDs are expected to be largely standardized across U.S. health care systems. However, this is a claims database and only the insured and beneficiaries who have Supplementary Medicare will be included in the database.

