## 6. VARIABLES

# 6.1. Exposure

The exposure of interest is the receipt of RZV (1-dose or 2 RZV doses at least 28 days apart).RZV vaccination will be identified from administrative and claims data by means of Current Procedural Terminology (CPT) code 90750 and National Drug Code (NDC) codes 58160-828-01, 58160-829-01, 58160-819-12, 58160-828-03, 58160-829-03, and 58160-823-11 (Appendix 4, Sections 13.4.3, 13.4.4, 13.4.5). Additional codes may be included for identification of RZV vaccination if relevant codes become available in the future.

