Presence of co-morbidities: kidney disease, cardiovascular disease, pulmonary disease [i.e., chronic obstructive pulmonary disease or chronic bronchitis, asthma], liver disease, diabetes mellitus, other autoimmune diseases, cancer, immunocompromising conditions [i.e., human immunodeficiency virus, cancer, transplant, immune-suppressive medications], SARS-CoV-2 infection/COVID-19 diagnosis with an index date after 2020) in the 365 days prior to the index date [Kawai, 2017a; Marra, 2020; Tsai, 2017; Yun, 2016].

Concomitant vaccinations during baseline: Influenza vaccine, tetanus, diphtheria and pertussis vaccine, pneumococcal vaccine in the 365 days prior to the index date, as a proxy for health behaviors.

Region of residence within U.S. as defined by the Census Bureau (4 regions: West, Midwest, South, Northeast) most recently prior to the index date [Izurieta, 2021; Sun, 2021].

Use of preventative services: screening, preventative visits in the 365 days prior to the index date [Izurieta, 2021].

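### Influenza vaccination, a named health-behaviour proxy, is captured from CPT/HCPCS codes only, while RZV is captured from CPT and pharmacy NDC codes; this can leave some healthy-user bias in VE

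*Protocol*

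**What the plan says.** **Exposure.** Section 6.1 identifies RZV "by means of Current Procedural Terminology (CPT) code 90750 and National Drug Code (NDC) codes". Section 13.4.3 gives the lists in two parts: "The following Current Procedural Terminology (CPT) code will be used to retrieve Shingrix vaccinations" (90750), then "The following National Drug Codes (NDCs) codes will be used to retrieve Shingrix vaccinations" (six NDCs).

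**Covariate.** Section 13.4.4 is headed "CPT/HCPCS codes used to identify influenza vaccinations". It holds 20 codes, all CPT or HCPCS.

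**Role of the covariate.** On healthy-user bias, section 5.2.1 (item 7) states: "The study will capture and adjust for variables related to healthy users, such as use of other vaccinations, to minimize this bias". Section 6.3 names the baseline vaccinations: "Influenza vaccine, tetanus, diphtheria and pertussis vaccine, pneumococcal vaccine in the 365 days prior to the index date, as a proxy for health behaviors". It also lists "Use of preventative services: screening, preventative visits in the 365 days prior to the index date", together with medical encounters and healthcare cost level. Of the three vaccines, only influenza has a code list in the protocol.

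**How the data arrive.** Section 3.1 places CPT and HCPCS codes on medical claims. Its account of pharmacy claims mentions no procedure code, and dispensing records are identified by NDC (section 3.1 and Appendix 3). Section 11.3.6 treats the covariates other than demographics and cost as yes/no variables.

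**Use in the analysis.** Under section 7.6, after exact matching on age band and medication category, the three comparators with the closest propensity score are chosen. Balance is judged by a standardized difference of 0.2, and covariates still imbalanced enter the Cox model.

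**The concern.** The plan searches pharmacy claims for the exposure but not for this confounder. On the protocol's own description of the data, an influenza shot billed solely by NDC leaves no code on the 13.4.4 list, and with a yes/no variable it becomes 'No' rather than missing.

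RZV recipients are likely to be more health-seeking than comparators; that is the premise of item 7. If part of their influenza vaccination is invisible, the propensity score treats them as less health-seeking than they are and pairs them with comparators of whom fewer were truly vaccinated. Item 7 says healthy users may show lower HZ rates, so what remains uncontrolled would push VE upwards.

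The safeguard in section 7.6 cannot detect this, because it is computed on the recorded variable. The error is also systematic: a larger cohort does not shrink it.

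**Working it through.** The protocol states no capture rate or bias figure, so there is nothing to reproduce. The code lists can be compared directly; the size can only be illustrated.

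**Step 1. Code lists compared.**

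| Variable | Medical claims (CPT/HCPCS) | Pharmacy claims (NDC) |
|---|---|---|
| RZV (6.1, 13.4.3) | 90750 | six NDCs |
| Influenza vaccine (13.4.4) | 20 codes | none |
| Pneumococcal; tetanus, diphtheria and pertussis (6.3) | no list in the protocol | no list in the protocol |

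**Step 2. Inputs, all assumed; the protocol gives none.**
- p1, true influenza uptake in RZV recipients: 0.70 to 0.80
- p0, true uptake in comparators: 0.50
- s, share of influenza shots captured, equal in both groups: 0.30 to 0.90
- r, HZ rate in influenza vaccinees relative to non-vaccinees: 0.7 to 0.9
- No false positives; comparators matched on recorded status; influenza the only adjuster

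**Step 3. Formula.** Among comparators recorded 'No', the share truly vaccinated is

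q0 = p0(1 − s) / (1 − p0·s).

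The factor by which the hazard ratio is multiplied is

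F = [1 − (1 − r)p1] / [p1·s·r + (1 − p1·s)(1 − (1 − r)q0)].

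Estimated VE = 1 − (true HR × F).

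**Step 4. Mid-case** (p1 = 0.80, s = 0.5, r = 0.8).
- q0 = 0.25 / 0.75 = 0.333
- Numerator: 1 − 0.2 × 0.80 = 0.84
- Denominator: 0.80 × 0.5 × 0.8 + 0.60 × (1 − 0.2 × 0.333) = 0.32 + 0.56 = 0.88
- F = 0.84 / 0.88 = 0.955
- True VE 60%: 1 − 0.4 × 0.955 = 61.8%. True VE 0%: 4.5%.

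**Step 5. Ends of the assumed range.**

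| p1 | s | r | F | True VE 60% reads | True VE 0% reads |
|---|---|---|---|---|---|
| 0.80 | 0.3 | 0.7 | 0.76 / 0.834 = 0.911 | 63.6% | 8.9% |
| 0.70 | 0.9 | 0.9 | 0.930 / 0.934 = 0.996 | 60.2% | 0.4% |
| any | 1.0 | any | 1.000 | 60.0% | 0.0% |

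**Step 6. Unequal capture.** With uptake 75% versus 50%, r = 0.8 and 40% missed in both groups, F = 0.85 / 0.879 = 0.97. If instead 60% is missed in RZV recipients and 40% in comparators, F = 0.85 / 0.90 = 0.94, and a true VE of 60% reads 62.2%.

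**Step 7. Why the balance check is blind.** In the mid-case, recorded uptake is 0.80 × 0.5 = 40% in RZV recipients and 40% in their matches, a standardized difference of 0. True uptake is 80% versus 0.40 + 0.60 × 0.333 = 60%. The true standardized difference is 0.20 / √[(0.16 + 0.24)/2] = 0.45, well above the 0.2 threshold.

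**The case against.** **Influenza vaccination is one proxy among several.** Section 6.3 adds two other vaccines, preventative services, encounters and cost, and item 7 offers other vaccinations only as an example. These variables are correlated, so they may recover part of what is missed. This stands. A reader might infer that the whole healthy-user control rests on influenza vaccination; the protocol does not say so.

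**The protocol does not say how pharmacy influenza shots are billed.** A shot claimed with a listed CPT or HCPCS code is captured wherever it was given. This stands too: only shots billed by NDC alone are lost, and their share is unknown. That every pharmacy shot is missed is a further inference the text does not support.

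**The shift is small beside sampling error.** Assume VE 60% with Tables 2 and 3, three comparators per recipient and no allowance for reuse of comparators. SLE gives 2910 × 1.3 × 0.01702 × 0.4 ≈ 26 vaccinated events and a 95% CI of roughly 40–74%. RA gives 15928 × 1.4 × 0.01553 × 0.4 ≈ 139 events and roughly 52–67%. A shift of one to four points is modest, though it does not shrink with cohort size.

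**Code lists are still open.** Section 2 makes defining code lists a study step, 13.4.4 does not exclude other sources, and an SAP could complete the covariates. A reader might take the absence under 13.4.4 of the note that codes will be updated as proof that the list is closed. It is not: sections 13.4.5 and 13.5 lack the note as well. But the protocol does state a capture method for influenza vaccination, and it is narrower than the one it states for RZV. That is more than detail left for later.

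**Residual confounding is disclosed in section 5.2.1.** True, but disclosure does not justify leaving an avoidable part of it.

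**Conclusion.** The asymmetry is in the text and should be removed. It can leave some residual healthy-user bias, in the direction of overstating VE, that the planned balance check would not reveal.

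Its size is not derivable from the protocol. Over the assumed ranges the hazard ratio is multiplied by about 0.91 to 0.996, so a true VE of 60% would read about 60.2% to 63.6%. These figures assume perfect specificity, equal capture in both groups and no help from the other proxies. Help from those proxies would shrink the bias; poorer capture among RZV recipients would enlarge it.

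Two stronger readings go too far. The documents do not show that VE is overstated in every cohort, because the share of shots billed by NDC alone is not given. Nor are RZV recipients recorded 'No' compared with people who were all truly unvaccinated: comparators recorded 'No' are a mixture (33% vaccinated in the mid-case), and matching is on the propensity score, not exactly on influenza status. This is an inexpensive improvement to confounder control, not a demonstrated failure of the primary analysis.

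**What to change.** - Add influenza vaccine NDCs to section 13.4.4 and search pharmacy claims for them over the same 365-day baseline.
- Define pneumococcal and tetanus/diphtheria/pertussis vaccination from both medical and pharmacy claims, on the same basis as RZV in section 6.1.
- Use the combined variables in the propensity score and in the balance tables.
- Optionally, report the share of influenza vaccinations found only by NDC, by RZV status. This would replace the assumed capture rates with observed data on the part the present list misses.

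The cost is a few additional code lists. Pharmacy claims are already in the database and already searched by NDC for RZV (13.4.3) and antivirals (13.4.5). No participants are lost and the design does not change.

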# 13.4.5. NDC Codes Used to identify herpes zoster antivirals

rug	NDCs
	00093363020, 00093894001, 00093894005, 00093894019, 00093894093, 00093894301, 00093894305, 00093894319, 00093894393, 00093894701, 00093894705, 00093894719, 00093894793,
	00168082515, 00168082530, 00172426660, 00172426670, 00172426760, 00172426770, 00172426860, 00172426870, 00182266600, 00182266689, 00182266700, 00182266789, 00182820000,
	00182820089, 00228260511, 00228260550, 00228260611, 00228260650, 00228260711, 00228260750, 00364269201, 00378025301, 00378025305, 00378030201, 00378146801, 00378220001,
	00378220005, 00378870006, 00378870049, 00378871273, 00395809719, 00395809762, 00440103030, 00440103130, 00440603001, 00440603005, 00440603030, 00440603060, 00440603081,
	00440603101, 00440603105, 00440603125, 00440603130, 00440603181, 00440603301, 00440603305, 00440603310, 00440603320, 00440603381, 00440703005, 00440703025, 00440703030,
	00440703050, 00440703060, 00440703081, 00440703083, 00440703085, 00440703089, 00440703125, 00440703130, 00440703181, 00440703185, 00440703189, 00440703310, 00440703320,
	00440703350, 00440703381, 00440703385, 00440703389, 00472008216, 00591033501, 00591033505, 00591033601, 00591033605, 00591115930, 00591269201, 00591269205, 00713063015,
	00713063031, 00904578961, 00904579061, 00904579961, 00904612161, 10544002640, 10544002725, 10544003925, 10544003940, 10544010125, 10544010225, 10544010240, 10544010340,
	10544014625, 10544014630, 10544015124, 10544015130, 10544015160, 10544020435, 10544020440, 10544020450, 10544094214, 10544094260, 12634069771, 13411018201, 13411018203,
	13411018206, 13411018209, 13411018210, 13411018301, 13411018303, 13411018306, 13411018309, 13411018310, 13668051501, 13668051502, 15455950001, 15455950002, 15455950003,
	15455950005, 15455950008, 15455950009, 1659000325, 16590000330, 16590000335, 16590000350, 16590000360, 16590037020, 16590037030, 16590037040, 16590037090, 16714066801,
	16714066802, 16714088501, 16714088502, 17236085301, 17236085401, 17856008205, 21695000925, 21695000930, 21695001015, 21695001020, 21695001021, 21695001025, 21695001030,
	21695001060, 21695001090, 21695001121, 21695001125, 21695001130, 21695001135, 21695001140, 23155014601, 23155022701, 23155022705, 23155022801, 23155022805, 23155022901,
	23155022905, 23490501101, 23490501201, 23490501202, 23490501203, 23490501204, 23490501301, 23490501302, 23490501303, 23490501304, 23490501501, 23490501501, 23490501502, 23490501503,
	23490501504, 23490501505, 23490501508, 31722077701, 31722077705, 31722077801, 31722077805, 33261022716, 33261022725, 33261022730, 33261022735, 33261022740, 33261022750,
	33261022760, 33261022790, 33261041930, 33261041960, 33261041990, 3326104918, 33261049130, 33261049160, 33261049190, 33358000925, 33358001015, 33358001028, 33358001030,
	33358001060, 33358001125, 33358001130, 33358001135, 35356090315, 35356090330, 35356090335, 35356090340, 35356090360, 35573040315, 35573040315, 35573040331, 38779017301, 38779017304,
	38779017305, 38779017308, 40085084296, 42254013315, 42254013320, 42254013321, 42254013325, 42254013330, 42254013360, 42254013390, 42254019821, 42254019826, 42254019830,
	42254019835, 42254019840, 42254019850, 42254031325, 42254031330, 42254031390, 42291001701, 42291001750, 42291010701, 42291010750, 42291010850, 422910010850, 422910010850, 422910010850, 422910010850, 422910010850, 422910010850, 422910010850, 422910010850, 422910010850, 42291010850, 42291010850, 42291010850, 42291010850, 42291010850, 42291010850, 42291010850, 42291010850, 42291010850, 422910010850, 422910010850, 422910010850, 422910010850, 422910010850, 422910010850, 422910010850, 422
وأريمامي	42291010990, 43063000101, 43063020405, 43063034001, 43063034004, 43063034005, 43063034015, 43063034025, 43063034030, 43063034040, 43063034060, 43063058910, 43063058930,
yclovir	43063058935, 43063058950, 43063070135, 43063070150, 43063082605, 43063082650, 43063088801, 43063088882, 43063092815, 43063092825, 43063092830, 43063092840, 43063092860,
	43353093318, 45802004475, 47463000325, 47463000330, 47463000335, 47463000430, 49452000101, 49452000102, 49452000103, 49452000108, 49884056501, 49884056505, 49884056601,
	49884056605, 49884056701, 49884056705, 49999008600, 49999008621, 49999008625, 49999008630, 49999008690, 49999023110, 49999023115, 49999023130, 49999023135, 49999023140,
	49999038510, 49999038515, 49999038525, 49999038540, 50090059500, 50090059501, 50090059507, 50090059601, 50090059601, 50090059607, 50090063800, 50090063802, 50090064402,
	50090064403, 50090064404, 50090064405, 50090064406, 50090064409, 50090064500, 50090064501, 50090156702, 50090156705, 50090156706, 50090162400, 50090162402, 50090325002,
	50090325003, 50090325004, 50090325005, 50090325006, 50090325009, 50090325400, 50090325401, 50268006011, 50268006015, 50268006111, 50268006115, 50268006215,
	50383081016, 51079044701, 51079044720, 51079044821, 51079044820, 51079044921, 51079044920, 51079055067, 51079055068, 51079087601, 51079087621, 51079087701, 51079087721,
	51079087801, 51079087820, 51407014501, 51407014505, 51407014601, 51407014601, 5152067101, 51552067102, 51552067103, 51552067104, 51552067105, 51552067106, 51672136001,
	51672136002, 51927299400, 52372081101, 52372081102, 52372081103, 52372081104, 52544033501, 52544033601, 52959051725, 52959051730, 52959051700, 529590000000000000000000000000000000000
	52959054410, 52959054412, 52959054415, 52959054421, 52959054421, 52959054425, 52959054430, 52959054440, 52959054450, 52959054460, 52959067830, 52959067840, 52959067850, 53002000815,
	53002000821, 53002000830, 53002000860, 53002002710, 53002002715, 53002002720, 53002002725, 53002002730, 53002002735, 53002002750, 53002002760, 53002002760, 530020024525, 530020024530,
	53002024535, 53002024550, 53002024560, 53217018815, 53217018821, 53217018825, 53217018828, 53217018830, 53217018850, 53217018860, 53217031325, 53217031335,
	53217031340, 53217031350, 54348062025, 54348062030, 54348062035, 54348062050, 54348062625, 54348062630, 54348062650, 54348062710, 54348062715, 54348062730, 54569448200,
	54569448201, 54569448202, 54569448203, 54569448204, 54569448206, 54569448207, 54569472402, 54569476500, 54569476501, 54569476502, 54569476503, 54569476504,
	54569476505, 54569476506, 54569476509, 54569652700, 54569682701, 54569888000, 54569888100, 54569888101, 54569888200, 54569888201, 54668399600, 54868399601,
	54868399602, 54868399603, 54868399604, 54868399700, 54868399701, 54868399702, 54868399703, 54868399704, 54868399800, 54868399801, 54868399802,
	54868399803, 54868399804, 54868399805, 54868399806, 54868399807, 54868399808, 54868568700, 55045257100, 55045257104, 55045257106, 55045257108, 550452
	55045264803, 55045264806, 55048000325, 55048000330, 55048000335, 55048000470, 55289027305, 55289027310, 55289027330, 55289027335, 55289027350,
	55289027412, 55289027415, 55289046230, 55289046201, 55289046201, 55289046212, 55289046215, 55289046221, 55289046220, 55289046230, 55289046230, 55289046240,
	55289046260, 55289062910, 55289062920, 55289062930, 55289062930, 55289062940, 55289062950, 55370055507, 55370055607, 55370055608, 55370055707, 55370055709,

